5.1.2 Phase II

In the Phase II, patients will be treated at the MTD of entospletinib in combination with obinutuzumab, determined in the dose escalation part of the study. Patients will be assessed for efficacy and safety (CTCAE v.4.03) parameters. **Only patients with CLL/SLL will be enrolled on Phase II part of the study.**

Each patient will be treated for at least 12 cycles, or until a qualifying event (Section 5.4 – Duration of therapy). Both drugs will be administered during cycles 1-6 (starting with the run-in phase), and entospletinib alone will be administered during cycles 7-12. Any patient discontinuing study treatment prior to completion of the first cycle for reasons other than AEs related to the study drugs will be replaced.

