5.4 Duration of Treatment

In the absence of treatment delays due to adverse events, treatment will continue for at least 12 cycles (treatment with entospletinib may continue beyond 12 cycles, as noted elsewhere; obinutuzumab will be administered for 6 cycles) or until one of the criteria below applies.

- Disease progression
- Unacceptable adverse event(s),
- Intercurrent illness that prevents further administration of treatment,
- Participant decides to withdraw from the study, or
- Pregnancy, or
- General or specific changes in the participant's condition render the participant unacceptable for further treatment in the opinion of the treating physician.
- Closure of study by sponsor investigator or discontinuation of drug availability.

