13.3 Analysis Population

Safety analysis set includes all patients who consent and take at least one dose of study drug, regardless of how long they stay on study drug. The end of treatment and early termination visit (see schedule) includes an evaluation of response at that visit. Reason(s) for going off study will be collected on every patient.

The dose-determining set (DDS) consists of a subset of patients in the safety analysis set who either meet the following minimum exposure criterion and have sufficient safety evaluations, during the first 1 cycle of dosing (including the run-in phase) or discontinue earlier due to DLT.

The efficacy-evaluable population will include all intent-to-treat (ITT) subjects who received at least 1 dose of study medication. Per protocol population will include all intent-to-treat (ITT) patients who completed 1 cycle of study treatment. The ITT subjects will include all subjects who are consented and enrolled in the Phase 2 Portion of the study.

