13.4.1 Analysis of Primary Endpoints

The MTD will be determined according to 3+3 dose escalation design using the dose determining set. Adverse events will be graded and categorized according to the CTCAE v4.03. All adverse events will be tabulated and summarized by major organ category, grade, anticipation, and drug attribution. SAE specific incidence and exact 95% confidence interval will be provided where appropriate.

The CR will be computed and presented together with the exact 95% confidence interval (CI), using the method of Clopper and Pearson. A null hypothesis of a 20% CR will be rejected if at least 7 of 17 patients achieve a CR and a treatment arm will not be considered further if this threshold is not reached.

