13.5 Sample Size and Power

Determination of phase I sample size

3+3 dose escalation scheme will be utilized, with 3 to 6 evaluated at each dose level. It is expected that maximum of 12 patients will be enrolled.

Determination of phase II sample size

Entospletinib has been associated with an ORR 61% at the end of study and obinutuzumab in combination with chlorambucil has led to an ORR of 77.3% and CR rate of 20.7% after completion of therapy [22]. The null hypothesis that the true CR rate is 20% will be tested against a one-sided alternative. A sample size of 17 achieves 83% power to detect a difference in complete response of 0.30 (0.2 vs. 0.5) using a one-sided binomial test with the target significance level of 0.05. The actual significance level achieved by this test is 0.0984. If more than equal to 7 patients achieve complete response, then conclude the regimen is effective, and consider a larger/next phase of clinical trial (phase III).

A sample size of 17 subjects treated at the RP2D provides a reasonable probability to detect a rare adverse event, for example, 83% chance of detecting an adverse event with an incidence of 10% (Table 14). Subjects with CLL treated at the RP2D in Phase I will be counted towards Phase II enrollment. Anticipating an attrition rate of 15%, a total of 20 patients per protocol population will need to be enrolled.

Table 14. Probability of detecting an AE with a specified incidence rate at the RP2D

AE incidence	N=17: Probability of detect an AE
0.01	0.16
0.05	0.58
0.10	0.83
0.15	0.94
0.20	0.98

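### The Phase II replacement rule leaves the CR denominator undefined, so more than 17 dosed patients can be judged against a cut-off built for 17, or early failures can be left out

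*Combined protocol and SAP*

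**What the plan says.** Section 5.1.2 provides that any Phase II patient "discontinuing study treatment prior to completion of the first cycle for reasons other than AEs related to the study drugs will be replaced". The same sentence closes section 5.1.1 for Phase I. Section 5.4 lists "Disease progression" first among the reasons for ending treatment, together with withdrawal and intercurrent illness. None of these is in itself a drug-related AE.

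Three other places bear on who is counted:

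- **Section 13.3:** "The efficacy-evaluable population will include all intent-to-treat (ITT) subjects who received at least 1 dose of study medication". Section 11.0 says the same. The per-protocol set is defined separately as ITT patients who completed one cycle.
- **Section 13.5:** after allowing 15% attrition, "a total of 20 patients per protocol population will need to be enrolled". It gives the decision rule without a denominator: "If more than equal to 7 patients achieve complete response, then conclude the regimen is effective".
- **Section 13.4.1:** "A null hypothesis of a 20% CR will be rejected if at least 7 of 17 patients achieve a CR". No analysis population is named, and no cut-off is given for any other number of patients.

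Section 13.7 imputes nothing and allows patients to be excluded for missing data if the reason is stated. It does not say how a replaced patient is counted.

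**The concern.** In Phase I the replacement sentence protects the DLT count, because a patient who leaves cycle 1 for an unrelated reason says little about toxicity. In Phase II the primary endpoint is CR, and the same sentence acts on efficacy outcomes. A patient who progresses, or dies of an unrelated cause, during the run-in or cycle 1 is a treatment failure, yet triggers a replacement.

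The plan then points two ways. Under 11.0 and 13.3 the replaced patient stays in, so more than 17 patients face a cut-off derived for 17. Under the per-protocol wording of 13.5 the patient drops out, and the denominator loses a failure. The replacement rule in fact matches neither population: a patient who stops in cycle 1 for a drug-related AE is not replaced, but is also outside the per-protocol set.

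This is the trial's only efficacy decision rule, and meeting it prompts consideration of a phase III trial. At this size one or two patients can change the answer, so the denominator should not be left for choice after the results are known.

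**Working it through.** **Inputs.** From 13.4.1 and 13.5: n = 17, cut-off 7, null CR rate 0.20, alternative 0.50, one-sided target 0.05, attrition 15%, enrolment 20. The number of patients replaced is not given. One to three is an assumption, with three equal to 20 − 17.

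**Plan's own figures.** For X ~ Binomial(17, p):

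- Power: P(X ≥ 7 | p = 0.50) = 0.834, which reproduces the stated 83%.
- Error: P(X ≥ 7 | p = 0.20) = 0.0377. The stated actual level of 0.0984 does not reproduce. That is a separate matter and is not used here.
- Enrolment: 17 / (1 − 0.15) = 20, as stated.

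**Scenario 1: replaced patients never reach CR, and the CR rate among all dosed patients is 20%.** Replacement continues until 17 patients remain. With n dosed, the CR rate among those 17 is 0.20 × n / 17, and the error is P(X ≥ 7 | 17, 0.20 × n / 17).

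| Dosed n | CR rate in the 17 | Error |
|---|---|---|
| 18 | 0.212 | 0.050 (0.0498) |
| 19 | 0.224 | 0.064 |
| 20 | 0.235 | 0.082 |

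Keeping or dropping the replaced patients does not change the number of CRs, so with the cut-off fixed at 7 the error is the same either way. What changes is the reported rate: seven CRs is 7/17 = 41.2% (exact 95% CI 18.4 to 67.1%) or 7/20 = 35.0% (15.4 to 59.2%).

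**Scenario 2: every dosed patient has a 20% chance of CR, and the cut-off stays at 7.** The error is P(X ≥ 7 | n, 0.20).

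| Dosed n | Error, cut-off 7 | Error, cut-off 8 | Power at 0.50, cut-off 8 |
|---|---|---|---|
| 18 | 0.051 | 0.016 | 0.76 |
| 19 | 0.068 | 0.023 | 0.82 |
| 20 | 0.087 | 0.032 | 0.87 |

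If only 17 of the dosed patients can reach CR, each with a 50% chance, power at cut-off 8 is P(X ≥ 8 | 17, 0.50) = 0.69 whatever n is.

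**The case against.** The efficacy-population text favours keeping replaced patients in: 11.0 and 13.3 agree, and replacement need only mean that another patient is enrolled. The sole support for dropping them is the per-protocol phrase in 13.5, which concerns enrolment. This stands. It makes the first reading likelier, but it does not supply a cut-off for 18 to 20 patients or a population for 13.4.1.

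The number affected may be very small. The early withdrawals that section 2.3.2.2 reports for relapsed CLL on obinutuzumab (3 of 20 in one Phase II cohort, 1 of 5 in another study) were infusion reactions. Those would be drug-related AEs and so would not be replaced. Lymphocytosis alone does not count as progression under 11.2.1. The plan's 15% is total attrition, and the step from 17 to 20 may itself be the allowance for replacements. All of this stands, and it limits how much weight the upper figures can bear.

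It may also be said that with 20 fully treated patients the mismatch arises from 13.5, not from replacement. That is fair for Scenario 2. The same statement of population and cut-off cures both.

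Three stronger readings are tempting and are not supported:

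- A reader might infer that an early stopper cannot be a CR because the first on-treatment CT is at C4D1. Under 5.5 and Table 10, patients who stop without progression still have an End of Treatment CT and follow-up scans. CR after so little treatment is unlikely, but the schedule does not exclude it.
- A reader might treat the two scenarios as separate biases that add. They are alternative assumptions about the same patients.
- A reader might infer that a single replacement takes the error past 0.05. That depends on the assumption: 0.0498 in Scenario 1, 0.0513 in Scenario 2.

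**Conclusion.** The point holds as a gap in specification. The plan replaces early efficacy failures in a phase whose endpoint is CR, does not say how they count, and fixes a cut-off for 17 only. Followed as written, the one-sided error can rise from 0.038 to between 0.050 and 0.087 with one to three extra dosed patients, against a target of 0.05. It is at or barely above the target with one, and clearly above it with two or three.

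These figures rest on an assumed number of replacements, on a null CR rate of 20% among all dosed patients, and on one or other assumption about whether replaced patients can respond. With no replacements and 17 dosed, the error stays at 0.038. The documents do not show that early failures will be removed from the analysis, nor that 15% of patients will be replaced. The plan should be corrected, but this does not invalidate the design, and it does not require a ban on replacing dosed patients.

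**What to change.** - **13.4.1:** name all dosed CLL/SLL patients at the RP2D as the primary CR population. Count any patient without a documented CR, including one replaced under 5.1.2, as non-CR.
- **13.5:** remove the reference to the per-protocol population, and state the cut-off for the number actually dosed: at least 7 for 17, and at least 8 for 18, 19 or 20 (error 0.016, 0.023 and 0.032).
- **5.1.2:** replacement may continue, with a statement that replaced patients stay in the denominator.
- **Sensitivity analysis:** report the CR rate among cycle-1 completers.

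The change adds no patients or procedures. It does have a cost. The reported CR rate will be slightly lower, and power should be restated: with a cut-off of 8 it is 0.76, 0.82 and 0.87 for 18, 19 and 20 dosed if each has a 50% chance of CR, and as low as 0.69 if only 17 of them can respond.

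Applying 7 to the first 17 dosed is an alternative, but it also costs power. With a 50% CR rate in completers and none in early stoppers, the overall rate is 0.50 × (1 − q) for an early-stopping share q. Power is then 0.78, 0.71 and 0.63 at assumed shares of 5%, 10% and 15%.

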5.2 Definition of Dose-Limiting Toxicities (DLT)

Dose escalation will stop for DLT defined as any of the following occurring with cycle 1 (including run-in) in the dose escalation phase, deemed related (possibly, probably or definitely) to the study drug:

1. Non-hematologic toxicity: all \geq Grade 3 toxicities *except*
 - a. Grade 3 nausea, vomiting or diarrhea reversible within 72 h with supportive care
 - b. Grade 3 infusion-related toxicity
 - c. Asymptomatic Grade 3-4 laboratory abnormalities that are reversible to \leq Grade 2 within 72 hours (for example, Grade 3-4 elevation of uric acid, AST, ALT, changes in phosphorus and magnesium levels, changes in glucose levels)
 - d. Grade 3 only: tumor lysis syndrome (TLS) or hyponatremia (equals Na 120-130 mEq/L)
2. Hematologic toxicity:
 - a. Grade 4 neutropenia lasting more than 7 days in a subject with ANC $> 1500 \mu\text{L}$ before beginning therapy
 - b. Febrile neutropenia of any duration (ANC $< 500/\mu\text{L}$, fever $> 38.5^\circ\text{C}$)
 - c. Grade 4 thrombocytopenia/anemia or grade 3 thrombocytopenia with bleeding or any requirement for platelet transfusion, unexplained by underlying disease

Grading of toxicities will be according to NCI CTCAE v.4.03. Grading of hematologic toxicity in patients with CLL/SLL will be conducted according to the 1996 modified NCI-WG criteria for CLL/small lymphocytic lymphoma (SLL), updated in 2008 [41]. A toxicity deemed to be unrelated to therapy (such as hip fracture due to a traumatic fall), will NOT be considered as a DLT.

Patients who completed 1 cycle of study treatment will be evaluable for dose escalation decision purpose. Patients who receive $< 50\%$ of doses of entospletinib or < 2 doses of obinutuzumab during cycle 1 and who do not experience DLT, will NOT be evaluable for dose escalation decision purpose and will be replaced. Intra-patient dose escalation will be allowed to the level of MTD, once MTD has been determined.

Management and dose modifications associated with the above adverse events are outlined in Section 6.

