6.0 DOSING DELAYS/DOSE MODIFICATIONS

6.1 Dose Modifications/Delays for Toxicities Encountered During Therapy.

Table 6. Dose Modifications and Delays for Entospletinib and Obinutuzumab

Description		Grade	Dose modification
Non-hematologic	Initial or first recurrence	3-4 and clinically significant*	Hold treatment with both drugs and evaluate at least weekly as clinically indicated. Delay dose until toxicity resolves to Grade ≤ 2 , then complete current cycle or start next cycle with reduction in entospletinib by one dose level (Table 5)
	Second recurrence		Discontinue
Description		Grade	Dose modification
Hematologic	Initial or first recurrence	As defined in DLTs: Grade 4 neutropenia lasting > 7 days. Grade 4 thrombocytopenia/ anemia or grade 3 thrombocytopenia with bleeding or any requirement for platelet transfusion, unexplained by underlying disease Febrile neutropenia	Hold treatment with both drugs. Initiate at least weekly CBC checks, growth factor (G-CSF allowed at Investigator's discretion) and transfusion support as clinically indicated until resolved to Grade 1 or $> 75\%$ baseline. May continue this cycle or start next cycle with reduction in entospletinib by one dose level (Table 5).
	Second recurrence		Discontinue

*Not clinically significant includes: Grade 3 nausea or vomiting occurring without optimal treatment; asymptomatic Grade 3 laboratory abnormalities that are not life-threatening and respond to treatment; grade 3 obinutuzumab infusion reactions; grade 4 infusion reaction, which will be an investigator dependent decision

Note: Grading of non-hematologic toxicities will be according to NCI CTCAE v.4.03. Grading of hematologic toxicity will be according to the 1996 modified NCI-WG criteria for CLL/SLL, updated in 2008.

Table 7. Restarting Doses of Entospletinib after Treatment Interruption for Drug-Related Toxicity

Entospletinib dose at the time of first toxicity	1 st reduction	2 nd reduction
200 mg daily	Discontinue	-
200 mg BID	200 mg daily	Discontinue
400 mg BID	200 mg BID	200 mg daily

There are NO dose reductions for obinutuzumab.

In cases where toxicities led to dose reduction, dose re-escalation of entospletinib may be considered in subsequent cycles at the discretion of the treating physician after at least two cycles of study therapy are well tolerated without any recurrent toxicities at the reduced dose.

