Treatment delays due to hematologic, non-hematologic and renal toxicities are permitted for up to 28 days from the end of a previous 28-day cycle. For longer delays, the study treatment will end (Section 5.5). In case of a treatment delay subsequent study assessment days will be adjusted accordingly. If a treatment delay occurs, both drugs (entospletinib and obinutuzumab) will be delayed.

For less severe toxicities not described above, holding one or both drugs and dose reductions are discouraged, but remain at the discretion of the treating physician.

Treatment with entospletinib and obinutuzumab will be discontinued if one of the following occurs despite dose modifications:

1. Second recurrence of grade 3-4 non-hematologic toxicities.
2. Second recurrence of grade 3-4 hematologic toxicities.
3. Treatment delay of >28 days from the end of a previous 28-day cycle.

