13.1 Study Design

Phase I Study Design

This is an open-label, phase I/II, dose-finding study in which safety and tolerability of escalating doses SYK inhibitor entospletinib (GS-9973) in combination with obinutuzumab in patients with relapsed/refractory chronic lymphocytic leukemia/small lymphocytic lymphoma (CLL/SLL) and NHL (FL, MCL, LPL, MZL). Since best responses for both entospletinib and obinutuzumab have been documented in CLL/SLL, the Phase II portion of the study will be limited to those patients, however additional expansion cohorts may be considered at a later date.

For the dose finding part of the study, Dose escalation will proceed within each cohort according to the following scheme. Dose-limiting toxicity (DLT) is defined in the section 5.2. The starting dose of entospletinib will be 200 mg po bid daily with one dose escalation (dose level 2) and 1 dose de-escalation. Entospletinib will be administered as a single agent for 7 days prior to C1D1 to allow for assessment of biomarkers.

Table 13. Dose levels planned for dose escalation phase of the study

Dose Level	Entospletinib (Cycles 1-12)	Obinutuzumab (Cycles 1-6) IV
-1*	200 mg daily	C1D1 – 100 mg; C1D2 – 900 mg
1	200 mg BID	C1D8 & 15 – 1000 mg
2	400 mg BID	C2-6 – 1000 mg on day 1

*Dose Level -1 will be studied only if more than one patient develops a DLT in Dose Level 1

Determination of MTD

The dosage will follow the 3+3 traditional escalation rules, starts with 3 cohorts at a planned dose level. If 0 out of 3 patients experiences DLT, dose will be escalated to the next higher level at which 3 cohort will be enrolled. If 1 out of 3 patients experiences DLT, 3 more patients will be enrolled at the same dose level. Escalation will continue if 1 of 6 patients experiences a DLT. If 2 or more patients in any dose level except for the starting dose level experience DLTs, dosing will stop, and previous dose level is determined to be MTD, unless only 3 patients have been treated at that level (the tentative MTD). If 2 or more patients in the starting dose level experience DLT, dose will be de-escalated to the -1 dose levels. A tentative MTD becomes final when a total of 6 patients are treated with less than 2 DLT, or a total of 3 patients are treated with less than 1 DLT.

Phase II Study Design

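### The evaluability floor in 5.2 counts entospletinib doses of any size, so a Level 2 patient reduced to 200 mg BID can still count as DLT-free at 400 mg BID

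*Combined protocol and SAP*

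**What the plan says.** Section 5.2 gives a positive rule: "Patients who completed 1 cycle of study treatment will be evaluable for dose escalation decision purpose". A DLT-free patient is set aside and replaced only when taking less than 50% "of doses of entospletinib or < 2 doses of obinutuzumab during cycle 1 and who do not experience DLT". Nothing refers to milligrams or to staying at the assigned level. The DLT window includes the run-in; the floor names cycle 1 only.

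Section 5.2 also exempts some related Grade 3 events from being DLTs, among them "Grade 3 nausea, vomiting or diarrhea reversible within 72 h with supportive care". It then adds: "Management and dose modifications associated with the above adverse events are outlined in Section 6".

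In Section 6.1, Table 6 holds both drugs for a clinically significant Grade 3-4 non-hematologic event, and the instruction continues "then complete current cycle or start next cycle with reduction in" entospletinib by one dose level. Its footnote lists events that are not clinically significant. The list includes "Grade 3 nausea or vomiting occurring without optimal treatment" but does not mention diarrhea. For milder toxicity, "dose reductions are discouraged, but remain at the discretion of the treating physician". Under Table 7 the first step down is 400 mg BID to 200 mg BID, or 200 mg BID to 200 mg daily.

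Sections 5.1.1 and 5.1.2 provide for replacing patients who discontinue, not patients whose dose is reduced. Section 13.3 defines the dose-determining set by a minimum exposure criterion that it never states, and 13.4.1 takes the MTD from that set. In Table 3, 0/3 or 1/6 DLTs at Level 2 opens Phase II at that dose. Section 13.1 lets a tentative MTD become final when "a total of 3 patients are treated with less than 1 DLT". It also returns the study to Phase I if two or more of the first six subjects at the MTD, Phase I patients included, have a DLT.

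**The concern.** A 3+3 decision reads each DLT-free patient as evidence about the dose of the cohort. If such a patient took the Level 1 dose for most or all of the combination cycle, the evidence belongs to Level 1 but is credited to Level 2. With three patients enough to open Phase II at 400 mg BID, one misattributed patient is a third of the basis for the decision.

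The route is in the text. An example is Grade 3 diarrhea on Day -5 that resolves within 72 hours. It is not a DLT and is not on the footnote's list, and cycle 1 may then start at 200 mg BID. Nausea or vomiting despite optimal treatment that reverses within 72 hours, or a discretionary reduction, leads to the same place. The floor is also uneven: Level 1 steps down from twice daily to once daily, so there the dose count does fall with the milligrams.

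**Working it through.** The plan gives no figure on this point, so there is none to reproduce.

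**Step 1: exposure in cycle 1.** Inputs: 28-day cycle and BID dosing (5.1.1), so 56 doses; at 400 mg, 56 × 400 = 22,400 mg. Reductions follow Table 7. Let f be the days at full dose, h the days held, and the remaining days one level lower.

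- Level 2: doses = 2(28 − h); mg = 800f + 400(28 − f − h).
- Level 1: doses = 2f + (28 − f − h) = 28 + f − h, with the same percentage in mg.

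At Level 2 the floor acts only if 2(28 − h) < 28, that is h > 14. The number of full-dose days does not enter.

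| History | Level | Doses of 56 | Share of planned mg | Under 5.2 now |
|---|---|---|---|---|
| Reduced in run-in (f=0, h=0) | 2 | 56 (100%) | 11,200/22,400 = 50.0% | kept |
| Held C1D3-D7, then reduced (f=2, h=5) | 2 | 46 (82%) | 10,000/22,400 = 44.6% | kept |
| Same hold and reduction (f=2, h=5) | 1 | 25 (44.6%) | 44.6% | replaced |
| Reduced from C1D8, no hold (f=7, h=0) | 2 | 56 (100%) | 14,000/22,400 = 62.5% | kept |
| Reduced in run-in (f=0, h=0) | 1 | 28 (50.0%) | 50.0% | kept, as not below 50% |

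The second and third rows are the same clinical history, handled in opposite ways at the two levels.

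**Step 2: effect on the decision.** Let p be the true DLT probability at 400 mg BID (assumed; the documents give none) and q = 1 − p. Level 2 passes both the 3+3 rule and the return rule if at most one of the first six patients has a DLT.

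- All six fully exposed: q⁶ + 6pq⁵.
- One of the first three unable to show a DLT (upper bound): q⁵ + 5pq⁴.
- That patient at half the risk: (1 − p/2)(q⁵ + 5pq⁴) + (p/2)q⁵.

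| p | All exposed | Half risk | Upper bound |
|---|---|---|---|
| 0.20 | 0.262 + 0.393 = 66% | 0.9 × 0.737 + 0.1 × 0.328 = 70% | 0.328 + 0.410 = 74% |
| 0.33 | 0.090 + 0.267 = 36% | 0.835 × 0.468 + 0.165 × 0.135 = 41% | 0.135 + 0.332 = 47% |
| 0.40 | 0.047 + 0.187 = 23% | 0.8 × 0.337 + 0.2 × 0.078 = 29% | 0.078 + 0.259 = 34% |

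The upper-bound gap is about 8 to 11 percentage points.

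**The case against.** The strongest reply is that the route is narrow. Most related Grade 3 or higher non-hematologic events are DLTs. What remains is mainly gastrointestinal events that reverse within 72 hours, which the investigator must still judge clinically significant, and reductions that 6.1 discourages. The documents give no cycle 1 rate of Grade 3 diarrhea. Section 2.2.4 gives all-grade diarrhea (40.8%), and 5.3.7 gives Grade 3 nausea below 4% in a Phase II study. This stands: the event is probably uncommon.

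Table 6 can also be read as finishing the current cycle at the same dose and reducing only at the next. On that reading its mid-cycle reductions fall away, and a run-in event turns on whether C1D1 begins a next cycle. The text does not settle this, and the discretionary reduction would remain. One could likewise read doses in 5.2 as doses at the assigned level, but nothing says so.

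Three stronger readings are tempting and not supported:

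- **That tumor lysis syndrome is a further route.** Section 5.3.1 defines Grade 3 TLS by serum values alone, which the Table 6 footnote largely covers when the patient is asymptomatic and responds to treatment. Its clinical manifestations are Grade 4, which 5.2 does not exempt.
- **That the return rule gives no protection.** It counts only DLTs, and the reduced patient fills one of its six places, but after 0/3 it still scores three more patients. Leaving it out gives 71% to 80%, 43% to 58%, and 31% to 46%, which overstates the gap.
- **That nothing else stands before Phase II.** Section 13.4.4 requires a safety review after dose finding, where reductions could be seen, although it sets no criterion for them.

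**Conclusion.** The point holds as a gap in the evaluability rule. As written, 5.2 can credit a patient to 400 mg BID who took no 400 mg dose together with obinutuzumab, and it replaces at Level 1 a history that it keeps at Level 2. Neither 13.3 nor the replacement rules close the gap.

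The increases of 8 to 11 points are an upper bound. They are conditional on such a patient being among the first three, on that patient having no chance of a DLT despite the run-in and 200 mg BID with obinutuzumab, and on assumed DLT rates. At half the risk the gap is about 4 to 6 points. The unconditional effect is smaller again, by an unknown frequency. A reader might infer that the plan is likely to select too high a dose, or that the CR analysis is affected; the documents support neither. This is an inexpensive improvement to a rule, not a fault that undermines the design.

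**What to change.** In 5.2, keep the 50% figure, the obinutuzumab condition and the replacement convention, and change only the entospletinib term so that a patient is non-evaluable when receiving *< 50% of the planned cycle 1 doses of entospletinib at the assigned dose level*. State the same criterion in 13.3 where the minimum exposure criterion is announced.

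At Level 2 the count becomes 2f of 56 when no full-level doses are missed. The run-in case gives 0 of 56, the C1D3-D7 hold gives 4 of 56 (7%), and a reduction from C1D8 gives 14 of 56 (25%); all are replaced. A reduction from C1D15 gives 28 of 56 (50%) and is kept, with (800 × 14 + 400 × 14)/22,400 = 75% of planned milligrams. Simply changing the unit to milligrams would not serve: the run-in case falls at exactly 50.0%, so a floor of less than 50% misses it, and the C1D8 case stands at 62.5%.

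The cost is an occasional replacement patient. Replacement also takes a drug-related intolerance out of the dose-determining set. The patient stays in the safety analysis set, and every reduction inside the DLT window should be reported at the 13.4.4 review.
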